### **5.12.1 Procedures for Discontinuation**

If a subject prematurely discontinues the study prior to the Month 12 (Visit 11) visit (excluding subjects enrolling in INS-312), the subject will have:

- EOT visit

Protocol Amendment #3 version: 22 February 2016

*This protocol is solely for the purpose of communicating information about the investigational drug between Insmmed Incorporated and study personnel. Information is not to be reproduced, abstracted or used for sharing of information for any other purpose, whatsoever, except with the written permission of Insmmed Incorporated.*

- Telephone contact 28 days after the EOT visit for safety follow-up
- Telephone contact at Month 12 (time point from Baseline) for safety follow-up (if not coinciding with the 28 day after EOT telephone contact)
- Telephone contact 12 months after the EOT visit for vital status and safety follow-up

If a subject prematurely discontinues the study on or after the Month 12 visit, the subject will have:

- EOT visit
- Telephone contact 28 days after the EOT visit for safety follow-up
- Telephone contact 12 months after the EOT visit for vital status and safety follow-up

If a subject prematurely discontinues the study during the off-treatment phase (after completion of 12 months of treatment), the subject will have:

- Telephone contact at the 12 Month Safety Follow-Up visit for vital status and safety follow-up

Subjects who are part of the sputum PK subset who discontinue LAI at any time point will have to return for clinic visits 28 days and 3 months off-LAI for sputum PK and sputum culture collection.

## 6 STUDY PROCEDURES

### 6.1 SCREENING VISIT (VISIT 1)

None of the following procedures or assessments can be made until the subject has provided informed consent as documented on the Informed Consent Form (ICF).

After informed consent has been obtained, all of the following will be performed:

- 12-lead ECG (see [Section 7.2.5](#))
- obtain medical history (this can be done anytime between Screening and Baseline and the information will only be entered into the EDC system once a subject has been enrolled into the study)
- administer physical examination, including vital signs and pulse oximetry (see [Section 7.2.2](#) and [Section 7.2.3](#))

Protocol Amendment #3 version: 22 February 2016

*This protocol is solely for the purpose of communicating information about the investigational drug between Insmmed Incorporated and study personnel. Information is not to be reproduced, abstracted or used for sharing of information for any other purpose, whatsoever, except with the written permission of Insmmed Incorporated.*

- administer audiology test (may be administered either at the Screening or Baseline [Day 1] visit, not both; see [Section 7.2.9](#))
- soliciting of concomitant medications (see [Section 7.2.8](#)) (this can be done anytime between Screening and Baseline and the information will only be entered into the EDC system once a subject has been enrolled into the study)
- collect sputum specimen for microbiological assessment (see [Section 7.1.1](#))
- collect blood or urine specimens for clinical chemistry, hematology, and urinalysis testing and, for women of child-bearing, a human chorionic gonadotropin (hCG) pregnancy test (see [Section 7.2.7](#))
- dispense sputum collection containers (see [Section 7.2.7](#))
- subjects will collect 2 sputum samples at home during the week immediately following the Screening visit.

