- b The Screening window allows time for sputum culture results, minimum inhibitory concentration (MIC) determination, and scheduling of Screening assessments. Any delay in obtaining microbiological results and MICs must be reported to the Sponsor immediately and documented within the study source documents. In the event that sputum culture results are not known by 8 weeks (Day -14), the Baseline (Day 1) visit should be scheduled as soon as possible in order to maintain the Screening window, and an extension of the Screening window to 14 weeks is allowed, if necessary. If sputum culture results are known prior to 8 weeks (Day -14), the Screening window of 10 weeks must be maintained.
- c Serum pregnancy testing will be performed on women of child bearing potential at Screening. A urine pregnancy test will be performed on women of child bearing potential at all other visits. Women not of child bearing potential are defined as postmenopausal (i.e., amenorrheic for at least 1 year), or surgically or naturally sterile.
- d Vital signs and pulse oximetry will be assessed both before and after dosing on visits where study drug is administered.
- e The 6MWT must be conducted by a site member who is blinded to the subject’s open-label treatment assignment.
- f The PFTs will be performed at sites with access to spirometers and trained personnel to perform spirometry tests. See [Section 7.2.4](#).
- g The Baseline audiology examination must be performed during Screening period or on Day 1 before study drug administration.
- h At Baseline (Day 1), AEs will be assessed only after study drug administration or first dose of multi-drug regimen. Any AE that has occurred prior to the first dose must be included in the subject’s medical history, including any AEs that occur within the Screening period.
- i Only for subjects who agreed to participate in the CT Scan sub-study. A prior chest CT scan may be used as a subject’s Baseline (Day 1) measurement if this CT scan was obtained within 6 months from the subject’s Baseline (Day 1) visit. Subjects will have their follow-up chest CT scan at the EOT visit provided the last chest CT scan was not obtained within the prior 6 months. High resolution CT scan is preferred, if available. Please refer to [APPENDIX 4](#) for additional details on the CT Scan sub-study.

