#### **4.2 EXCLUSION CRITERIA**

A prospective patient with any of the following conditions must be excluded from this study:

1. patients with cystic fibrosis
2. patients whose MAC NTM infection is resistant to amikacin (as identified by MIC susceptibility  $>64 \mu\text{g/mL}$ )
3. patients who are not able to perform the 6MWT
4. positive pregnancy test or lactation at Screening. All women of child bearing potential will be tested. Women not of child bearing potential are defined as postmenopausal (i.e., amenorrheic for at least 1 year), or surgically or naturally sterile.
5. active pulmonary malignancy (primary or metastatic) or any malignancy requiring chemotherapy or radiation therapy within 1 year before Screening or anticipated during the study period
6. active allergic bronchopulmonary mycosis or any other condition requiring chronic systemic corticosteroids at a dose greater than the equivalent of 10 mg/day of prednisone within 3 months before Screening
7. active pulmonary tuberculosis requiring treatment at Screening
8. history of lung transplantation
9. initiation of chronic therapy (e.g., high dose ibuprofen, inhaled anti-inflammatory agents including steroids, low dose maintenance steroids, rhDNase) within 28 days before Day 1
10. administration of any investigational drug within 8 weeks before Screening

Protocol Amendment #3 version: 22 February 2016

*This protocol is solely for the purpose of communicating information about the investigational drug between Insmmed Incorporated and study personnel. Information is not to be reproduced, abstracted or used for sharing of information for any other purpose, whatsoever, except with the written permission of Insmmed Incorporated.*

11. prior exposure to LAI (including clinical study)
12. known hypersensitivity to aminoglycosides
13. use of inhaled or systemic aminoglycosides with activity against MAC (e.g., amikacin, kanamycin, or streptomycin) within 28 days before Day 1
14. acquired and primary immunodeficiency syndromes (e.g. HIV-positive patients regardless of CD4 counts)
15. significant (as determined by the investigator) hearing loss, vestibular dysfunction, neuromuscular weakness or a diagnosis of myasthenia gravis, where the potential risk of aminoglycoside toxicity outweighs the potential benefit
16. aspartate aminotransferase or alanine aminotransferase  $\geq 3$  times the upper limit of normal (ULN) or total bilirubin  $\geq 2$  times ULN at Screening

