## 5.10 PROHIBITED MEDICATIONS

Subjects are prohibited from using any inhaled antibiotics and any aminoglycosides with activity against MAC from 28 days before Day 1, and should not initiate these drugs during the study period unless clinically indicated as determined by the Investigator. If a subject requires an inhalational antibiotic for medical management of an acute pulmonary exacerbation secondary to Gram-negative bacteria during the study, then LAI should be interrupted during the course of that inhaled antibiotic treatment and until the acute event has resolved. Inhaled antibiotics such as tobramycin that do not have activity against MAC are permitted. Administration of LAI should begin again after the inhaled antibiotic is stopped and the acute event has resolved. During the course of an inhaled antibiotic treatment, the subject will remain in the study and complete all remaining study visits if possible. Exceptions include treatment with IV amikacin (or nebulized IV amikacin solution) and other aminoglycosides with activity against MAC, such as streptomycin or kanamycin. Such aminoglycosides for the treatment of NTM lung infection will be considered a “rescue” medication. If the Investigator believes that any of the aforementioned prohibited medications are necessary they must discuss these with the medical monitor and the subject will discontinue study drug and/or the study. Any questions about prohibited medications should be discussed with the medical monitor for the study.

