## 6.2 BASELINE VISIT (DAY 1, VISIT 2)

All of the following should be performed or obtained within 70 days after Screening unless the results of the sputum culture analysis are delayed. In the event that sputum culture results are not known by 8 weeks (Day -14), the Baseline (Day 1) visit should be scheduled as soon as possible in order to maintain the Screening window, and an extension of the Screening window to 14 weeks is allowed, if necessary. If sputum culture results are known prior to 8 weeks (Day -14), the Screening window of 10 weeks must be maintained.

- administer SGRQ before study drug administration (see [Section 7.3.1](#))
- administer EQ-5D-3L before study drug administration (see [Section 7.3.2](#))
- collect information on healthcare resource utilization
- update medical history
- administer physical examination, including vital signs and pulse oximetry. Only vital signs and pulse oximetry will be assessed both before and after study drug administration (see [Section 7.2.2](#) and [Section 7.2.3](#))
- administer 6MWT (see [Section 7.2.1](#))

Protocol Amendment #3 version: 22 February 2016

*This protocol is solely for the purpose of communicating information about the investigational drug between Insmid Incorporated and study personnel. Information is not to be reproduced, abstracted or used for sharing of information for any other purpose, whatsoever, except with the written permission of Insmid Incorporated.*

- administer the pulmonary function test prior to study drug administration (see [Section 7.2.4](#))
- administer audiology test (may be administered either at the Screening or Baseline [Day 1] visit, not both; see [Section 7.2.9](#))
- obtain CT chest scan if part of CT Scan Sub-Study and has not been acquired within 6 months before Day 1 (see [Section 7.3.4](#), [APPENDIX 4](#))
- obtain CT chest scan if part of Japan specific CT Scan Sub-Study and has not been acquired within 6 months before Day 1 (see [APPENDIX 5](#))
- solicit concomitant medications (see [Section 7.2.8](#))
- assess AEs (see [Section 8](#))
- collect sputum specimen for microbiological assessment (see [Section 7.1.1](#))
- collect sputum specimen for sputum-only PK sub-set analyses (see [Section 7.4.1](#))
- collect blood or urine specimens for clinical chemistry, hematology, and urinalysis testing and, for women of child-bearing, a urine pregnancy test (see [Section 7.2.7](#))

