## **7.2.9 Audiology**

### **7.2.9.1 Methodology**

Audiology testing will be performed either at Screening or before administration of study drug at Baseline (Day 1), before study drug administration at Months 3, 6 and 12, and the end of treatment visit. Frequencies of 250, 500, 1000, 2000, 4000, and 8000 Hz will be evaluated for each ear using air conduction. If post-Baseline (Day 1) audiometry findings are an AE Grade 2 or higher (according to the Common Terminology Criteria for Adverse Events [CTCAE] Version 4.0 guideline), an additional audiometric evaluation should be conducted at the next scheduled visit.

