### **7.2.9.2 Assessment**

Significant Baseline (Day 1) findings and all post-Baseline (Day 1) findings (including hearing loss of a CTCAE Grade 2 or higher) prior to first dose of LAI or multi-drug regimen on Day 1 must be recorded on the medical history page of the eCRF. Significant findings that meet the definition of an AE (including hearing loss of a CTCAE Grade 2 or higher) must be recorded on the AE page of the eCRF.

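### The only baseline audiogram may precede up to 42 or 70 days of permitted aminoglycoside use, so hearing lost in that interval can first appear as an on-study event

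*Protocol*

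**What the plan says.** **Baseline test.** Protocol Sections 6.1 (Screening) and 6.2 (Baseline) carry the same instruction: "administer audiology test (may be administered either at the Screening or Baseline [Day 1] visit, not both". Footnote g of Table 3-1 gives the permitted timing: "The Baseline audiology examination must be performed during Screening period or on Day 1 before study drug administration". Section 7.2.9.1 agrees. Neither the footnote nor 7.2.9.1 limits how old the audiogram may be on Day 1.

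**Screening window.** Section 6.2 sets the standard interval: "All of the following should be performed or obtained within 70 days after Screening". If culture results are late, "an extension of the Screening window to 14 weeks is allowed, if necessary". Table 3-1 shows the same range as 70 to 98 days before Day 1.

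**Aminoglycoside washout.** Exclusion criterion 13 in Section 4.2 bars "use of inhaled or systemic aminoglycosides with activity against MAC (e.g., amikacin, kanamycin, or streptomycin) within 28 days before Day 1". Section 5.10 uses the same limit: "Subjects are prohibited from using any inhaled antibiotics and any aminoglycosides with activity against MAC from 28 days before Day 1". Nothing bars such drugs between the Screening visit and Day −28.

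**Later tests and recording.** After baseline, audiometry is done "before study drug administration at Months 3, 6 and 12, and the end of treatment visit". Under Section 7.2.9.2, hearing findings "prior to first dose of LAI or multi-drug regimen on Day 1 must be recorded on the medical history page of the eCRF", and significant later findings that meet the adverse-event definition go on the adverse-event page. Section 8.3 lists ototoxicity among the adverse events of special interest.

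**The concern.** A baseline measurement for a drug-toxicity outcome should be taken after any earlier exposure to the same class of drug has ended. Here the washout is shorter than the screening window, and the site is told not to repeat a test already done at Screening. Together these rules let the baseline predate the end of a permitted ototoxic exposure.

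The situation is foreseeable. Subjects are refractory and may be on an ongoing multi-drug regimen at Screening, and criterion 13 itself names amikacin, kanamycin and streptomycin. A subject taking one of these at the Screening visit can still qualify by stopping in time for the washout.

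The protocol's sorting rule sends findings before the first dose to medical history and later ones to the adverse-event page. It works only if a loss can be seen before dosing. With one audiogram taken at the Screening visit, a loss that the subject has not noticed has no scheduled test to reveal it until Month 3. What is at stake is how well the counted rate of an adverse event of special interest reflects what happened on study, since audiometry is the only scheduled objective hearing test.

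**Working it through.** **1. The plan's own figures.** 10 weeks × 7 = 70 days and 14 weeks × 7 = 98 days, as in Table 3-1. Eight weeks into a 70-day window is 56 − 70 = Day −14, as stated. The screening figures are consistent with each other.

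**2. Permitted exposure after a Screening-visit audiogram.** This is the screening window minus the washout.
- Standard window: 70 − 28 = 42 days.
- Extended window: 98 − 28 = 70 days.
- Audiogram taken within the last 28 days before Day 1, or on Day 1 before dosing: 0 days.

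**3. Time to the next scheduled audiogram.** Taking Month 3 as about 90 days (an assumption), the gap from a Screening-visit test is 70 + 90 = 160 days to 98 + 90 = 188 days.

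**4. Effect on the arm comparison.** Let p be the true on-study risk in an arm. Let b be the proportion of subjects with an undetected pre-dose loss, the same in both arms because it precedes randomisation. If the two are independent:
- counted risk = 1 − (1 − p)(1 − b)
- counted risk difference = (1 − b)(p_LAI − p_control)

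If the true risks are equal, the counted difference is zero for any b. Illustration with assumed true risks of 2% (control) and 8% (LAI):

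| b | Control counted | LAI counted | Difference (points) | Ratio |
|---|---|---|---|---|
| 0% | 2.00% | 8.00% | 6.00 | 4.00 |
| 1% | 2.98% | 8.92% | 5.94 | 2.99 |
| 3% | 4.94% | 10.76% | 5.82 | 2.18 |
| 5% | 6.90% | 12.60% | 5.70 | 1.83 |

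With assumed true risks of 5% and 10%, raising b from 0% to 5% moves the difference from 5.00 to 4.75 points and the ratio from 2.00 to 1.49. In both settings the difference hardly moves and the ratio shrinks towards 1.

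**5. How large b might be.** The documents give no basis for it. Formally, b = (share tested before the exposure ended) × (share using such a drug in that interval) × (risk of unnoticed loss among them). Suppose every subject is tested at the Screening visit, 5–15% use such a drug afterwards and 5–10% of those lose hearing. Then b runs from 0.05 × 0.05 = 0.25% to 0.15 × 0.10 = 1.5%, or about 1 to 5 of 351 randomised subjects. All three inputs are assumptions, and the first is set at its maximum. The 3% and 5% rows above therefore exceed even this assumed range.

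**The case against.** The strongest case against acting is that several things must coincide. The site must test early in Screening. The subject must then take a MAC-active aminoglycoside, stop before the washout begins, lose hearing in that interval, and not notice the loss before Day 1. Sites can already avoid the problem, because the test may be done late in Screening or on Day 1. Medical history is updated and concomitant medications are asked about at Baseline, and adverse events seen before the first dose go to medical history. Causality is judged event by event with other drugs in view (Section 8.2.2), and Section 9.7 presents adverse events by relationship as well as by incidence.

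Most of this stands, and it limits how far the point can go. A reader might infer three stronger things that the documents do not support.

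- *Hearing loss from any earlier aminoglycoside is counted as LAI ototoxicity.* Loss already present at the audiogram is part of baseline. An adverse-event entry is defined by timing and is not a finding that LAI caused the event.
- *LAI will show a false excess.* The exposure precedes 2:1 randomisation and both arms follow the same audiometry schedule, so balance is expected. Open-label causality judgement could attribute such losses unequally, but the counts themselves are not biased against LAI.
- *Criterion 15 is judged on outdated hearing status.* That criterion rests on the investigator's judgement and, unlike criteria 16 to 18, is not tied to Screening or to the audiogram.

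What the objection does not remove is the instruction itself. For a subject already tested at Screening who then used an aminoglycoside, Sections 6.1 and 6.2 rule out the repeat test that would give a valid baseline. History and medication questions can reveal the exposure, but not a loss that no one has noticed.

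**Conclusion.** The point holds in a limited form. The baseline-audiogram rule and the aminoglycoside washout do not fit together: a Screening-visit audiogram leaves up to 42 days (10-week window) or 70 days (14-week window) of permitted exposure after the only baseline test. Unnoticed loss in that interval can be recorded as an on-study event when it is first detected at Month 3.

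The day counts follow directly from the protocol. The number of subjects affected cannot be derived from it, and the 1 to 5 subjects above rest wholly on assumed inputs. The expected effect is a somewhat higher counted rate in both arms, a nearly unchanged risk difference and a diluted ratio. For a safety outcome, dilution is not harmless, because it understates the relative risk. This is a cheap improvement to a measurement rule and does not threaten the trial's conclusions.

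**What to change.** In Sections 6.1 and 6.2, delete the words that forbid testing at both visits. In those two sections, in 7.2.9.1 and in footnote g of Table 3-1, add one conditional rule: a Screening audiogram serves as baseline only if no MAC-active aminoglycoside was used after it; otherwise the baseline audiogram is taken after the last aminoglycoside dose and before the first study dose. The Day 1 test before dosing, which the protocol already allows, meets this rule. The washout and the eligibility criteria need no change.

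The cost is amendment wording, less scheduling freedom, and an occasional repeat audiogram for the subjects who use an aminoglycoside during Screening. All others still have one baseline test.

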## 6.2 BASELINE VISIT (DAY 1, VISIT 2)

All of the following should be performed or obtained within 70 days after Screening unless the results of the sputum culture analysis are delayed. In the event that sputum culture results are not known by 8 weeks (Day -14), the Baseline (Day 1) visit should be scheduled as soon as possible in order to maintain the Screening window, and an extension of the Screening window to 14 weeks is allowed, if necessary. If sputum culture results are known prior to 8 weeks (Day -14), the Screening window of 10 weeks must be maintained.

- administer SGRQ before study drug administration (see [Section 7.3.1](#))
- administer EQ-5D-3L before study drug administration (see [Section 7.3.2](#))
- collect information on healthcare resource utilization
- update medical history
- administer physical examination, including vital signs and pulse oximetry. Only vital signs and pulse oximetry will be assessed both before and after study drug administration (see [Section 7.2.2](#) and [Section 7.2.3](#))
- administer 6MWT (see [Section 7.2.1](#))

Protocol Amendment #3 version: 22 February 2016

*This protocol is solely for the purpose of communicating information about the investigational drug between Insmid Incorporated and study personnel. Information is not to be reproduced, abstracted or used for sharing of information for any other purpose, whatsoever, except with the written permission of Insmid Incorporated.*

- administer the pulmonary function test prior to study drug administration (see [Section 7.2.4](#))
- administer audiology test (may be administered either at the Screening or Baseline [Day 1] visit, not both; see [Section 7.2.9](#))
- obtain CT chest scan if part of CT Scan Sub-Study and has not been acquired within 6 months before Day 1 (see [Section 7.3.4](#), [APPENDIX 4](#))
- obtain CT chest scan if part of Japan specific CT Scan Sub-Study and has not been acquired within 6 months before Day 1 (see [APPENDIX 5](#))
- solicit concomitant medications (see [Section 7.2.8](#))
- assess AEs (see [Section 8](#))
- collect sputum specimen for microbiological assessment (see [Section 7.1.1](#))
- collect sputum specimen for sputum-only PK sub-set analyses (see [Section 7.4.1](#))
- collect blood or urine specimens for clinical chemistry, hematology, and urinalysis testing and, for women of child-bearing, a urine pregnancy test (see [Section 7.2.7](#))
- collect blood (serum) specimen for biomarker assessment (CRP and IL-6) (see [Section 7.2.7](#))
- collect blood (serum) and sputum specimens for Comprehensive PK Sub-Study analysis in Japanese subjects only (see [Section 7.4.3](#) and [APPENDIX 3](#))
- dispense sputum collection containers (see [Section 7.2.7](#))
- administer study drug at the study site (see [Section 5.3](#))
- dispense study drug.

